[figure not shown]

[figure not shown]

## Sponsors

This study is funded by the NIH (1R01HD082302-01A1)

## II. SPECIFIC AIMS

The specific aims of this experiment are as follows:

[figure not shown]
- **Aim 1: To evaluate the efficacy of tDCS and mirror therapy (MT) as rehabilitative tools for the management of chronic PLP patients.**

We will explore the aim 1 in a randomized factorial controlled trial in which patients will be assigned to one of four groups: active tDCS and active MT; sham tDCS and active MT; active tDCS and sham MT (which consists of using a covered mirror for the therapy); and both sham tDCS and sham MT (covered mirror).

The primary end point will be severity of pain measured by changes in PLP as indexed by a Visual Analog Scale (VAS). The study will require a total of 13 weeks to be completed. The first week, each patient will give daily reports of their pain using a VAS, accounting for their PLP experience in the past 24hs. This initial baseline week will be followed by 4 weeks of treatment (tDCS and/or MT) and a final 8-week follow-up period without any treatment to examine long-lasting effects of each therapy. *Our hypothesis is that the combined intervention (tDCS and MT) will result in a greater pain reduction as compared with any therapy alone and no therapy.*

- **Aim 2: To examine the mechanisms underlying PLP using two neurophysiological techniques.**

For each of the four groups described in aim 1, we will determine the neural correlates of the effect. We will use single-pulse and paired-pulse transcranial magnetic stimulation (TMS) to assess cortical mapping and cortical excitability changes associated with cortical reorganization. We will also use functional magnetic resonance imaging (fMRI) to assess brain changes, including the quantification of maladaptive cortical reorganization. Using fMRI, we will determine the changes in Blood-Oxygen-Level dependent activation between the sensory-motor cortex of the affected and unaffected side after the treatment. We will compare these neurophysiological parameters before and after treatment in each of the four groups. *Our hypothesis is that the combined group (tDCS and mirror therapy) will have a greater activation than any therapy alone and also than the no therapy group (sham tDCS and covered mirror). This effect will also be correlated with pain reduction.*

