Each of these conditions will have the same length – 20 seconds. The fMRI session will have four runs that will contain 6 blocks (6 of each condition). The order of the conditions will be randomized. For the analysis we will determine the ROI of interest (primary sensory motor cortex of the lower limbs) and first determine the ratio of activation between the MOV-LEG and MIR-LEG (in the respective ROI of interest – contralateral to the respective leg). Using this coefficient we will then compare across the different conditions. Our hypothesis is that the combined group (tDCS and mirror therapy) will have a greater activation than any therapy alone

and also the no therapy group (sham tDCS and covered mirror). This effect will also be correlated with pain reduction.

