#### *For aim 1:*

[figure not shown]
The primary outcome is PLP indexed by VAS. PLP will be analyzed using intensity of pain over time. To analyze these data, we will initially build a mixed ANOVA model in which the dependent variable will be the outcome of PLP (such as VAS) and the independent variables will be group (active tDCS-MT; sham tDCS-MT; active tDCS and covered MT; sham tDCS- covered MT), time (baseline and after treatment and follow-up) and the interaction group\*time. In addition we will add the random variable ID to account for within subject’s variability and the repeated measures on time. We will initially perform this full model and, subsequently, post-hoc comparisons with corrections for multiple comparisons will be carried out initially to test our main hypotheses. Furthermore we will test the correlation in improvement between outcomes using Pearson’s correlation tests. P-values for secondary and exploratory outcomes will be determined without corrections for multiple comparisons. Finally we will apply a path analysis [60, 61] to the primary outcome data to determine if pain reduction associated with the combined intervention (tDCS and MT) is due to direct effects versus indirect effects through improvement in secondary outcomes. We propose that a direct effect of tDCS and MT on pain can be assumed if the treatment effect cannot be explained by changes in psychological or functional outcomes. Statistical models for pain will be developed using covariates that include site center, baseline

[figure not shown]
pain, psychological changes, functional changes, and the covariate treatment (main effect of treatment). To complete the path analysis separate regression models will be run to model the effects' of treatment on each outcome alone including all the secondary outcomes. Analyses of the secondary outcomes will be conducted in an exploratory manner (no correction for multiple comparisons). For the intention-to-treat analysis, we will use a conservative method and assume that participants will not improve from the last measured point. But we will also perform a sensitive analysis for the missing data using other methods such as completers only.

*For aim 2:*

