The secondary outcomes are other pain measurements, psychological, neuropsychological and quality of life measurements and neurophysiological markers (as indexed by TMS and fMRI). Functional neuroimaging data will be analyzed using both Freesurfer image analysis suite combined with the FS-FAST functional data analysis package (Massachusetts General Hospital, Charlestown, MA) (<http://surfer.nmr.mgh.harvard.edu/>) and with Brain Voyager QX 1.9 software package (Brain Innovation, Maastricht, Netherlands). Briefly, a high resolution anatomical T1-weighted anatomical volume is used to reconstruct a cortical surface mesh and then inflated to allow viewing of sulcal activation. The functional preprocessing includes 3-D motion correction using the first volume alignment, high pass filtering to remove temporal linear trends, correction for slice time acquisition and spatial smoothing (Gaussian kernel, 5.0 mm FWHM). Subjects are screened for excessive motion (defined as a maximum tolerance of 3mm in any direction). Following co-registration of the preprocessed functional image with the high-resolution anatomical, data is transformed into standard Talairach space. Voxel time courses for each subject are fit by a general linear model (GLM) for statistical analysis. Each experimental condition is modeled by a boxcar regressor matching the condition time course. These boxcar regressors are then smoothed by a canonical hemodynamic response function [62]. Individual subject maps for each contrast of interest is generated by projecting the volume of significance values resulting from the GLM onto the reconstructed cortical surface mesh for each hemisphere in each subject. Statistical significance is set at a standard threshold criterion of  $p < 0.05$  corrected for multiple comparisons using a cluster-size threshold adjustment [63].

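### Aim 2 states a between-arm hypothesis, but the comparison it describes is before versus after within each arm, and its analysis section specifies no between-arm model for TMS or fMRI

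*Combined protocol and SAP*

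**What the plan says.** II. Specific Aims, Aim 2, describes the comparison of TMS and fMRI measures as follows: "We will compare these neurophysiological parameters before and after treatment in each of the four groups". The hypothesis given straight afterwards is between arms: "the combined group (tDCS and mirror therapy) will have a greater activation than any therapy alone and also than the no therapy group".

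The fMRI text under Description of Assessments defines a ratio of activation between two leg-movement tasks and continues: "Using this coefficient we will then compare across the different conditions". It then repeats the between-arm hypothesis.

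In VI. Biostatistical Analysis, the text for aim 1 sets out a mixed model with group, time and their interaction, written for phantom limb pain. Later, as part of the path analysis, it plans a set of regressions for the influence "of treatment on each outcome alone including all the secondary outcomes". It also says: "Analyses of the secondary outcomes will be conducted in an exploratory manner (no correction for multiple comparisons").

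The text for aim 2 counts "neurophysiological markers (as indexed by TMS and fMRI") among the secondary outcomes. The rest describes fMRI preprocessing, a general linear model fitted to each subject's voxel time courses, and a cluster-size threshold.

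**The concern.** The hypothesis concerns differences between randomised arms. The comparison as worded asks, arm by arm, whether a marker moved from its baseline. An analyst could report four sets of within-arm p-values, find the combined arm significant and another arm not, and describe that as a superior mechanism while still following the Aim 2 wording.

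Each arm's change also contains whatever happens without a treatment effect: passage of time, repeat testing and any regression to the mean. For example, TMS intensity is tuned at baseline to give a motor evoked potential of about 1 mV and is then held constant, so later amplitudes can drift from the tuned value in every arm. The double-sham arm can remove such effects only if it is subtracted.

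Aim 2 is one of only two aims, and its conclusions about mechanism depend on this comparison.

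**Working it through.** **1. What each section supplies for the Aim 2 hypothesis**

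- II. Specific Aims: a before-after comparison per arm; no between-arm test.
- Description of Assessments, fMRI: a comparison across conditions. In that section the numbered conditions are the two movement tasks and rest, but the arm hypothesis follows at once, so the word could mean arms. No model is given, and TMS is not covered.
- For aim 1, mixed model: group, time and their interaction, for pain only.
- For aim 1, path analysis: treatment regressed on every secondary outcome. This reaches TMS and fMRI through the list under For aim 2. It does not say which form of the marker is the dependent variable, how that marker's baseline enters, or which arms are contrasted.
- For aim 2: no arm term, arm-by-time term or between-arm contrast, and no statistical model for TMS.

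**2. Why the two comparisons differ**

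Write the true mean change in arm k as θ + τ_k, where θ is the part common to all arms and τ_k is the treatment effect. A within-arm test asks whether θ + τ_k = 0. The hypothesis asks whether τ_combined − τ_j > 0 for each of the three other arms j. Only the between-arm difference removes θ.

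**3. Illustration**

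Assumptions: independent arms, the same true change in all four, and within-arm power p of 0.50, 0.65 or 0.80. The documents give no standard deviation for change in any TMS or fMRI marker, so p cannot be derived from them.

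Combined arm significant, one given comparator not: p(1 − p)

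- 0.50 × 0.50 = 0.250
- 0.65 × 0.35 = 0.228
- 0.80 × 0.20 = 0.160

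Combined arm significant, all three comparators not: p(1 − p)³

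- 0.50 × 0.125 = 0.063
- 0.65 × 0.0429 = 0.028
- 0.80 × 0.008 = 0.006

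**4. Sample size**

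The primary calculation reproduces. The pooled SD is √((1.5² + 1.6²)/2) = 1.551 and the difference is 6.4 − 5.2 = 1.2. Then n = 2 × (1.551 × (1.960 + 0.842)/1.2)² = 26.2, so 27 per arm and 108 in total. With attrition, 27 × 1.2 = 32.4, so 33 per arm and 132. None of this depends on Aim 2.

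For fMRI, the plan says only that 7 to 8 subjects suffice. It does not say whether that is per arm or in total, or for a within-arm or between-arm change. If it means a paired test in one arm at 80% power and two-sided 5% (an assumption), the detectable change is 1.27 SD (n = 7) or 1.16 SD (n = 8) of the change score. A two-sample t-test for a between-arm difference of that same size would have 59% or 58% power with 7 or 8 per arm. With 27 per arm, the between-arm difference detectable at 80% power is 0.78 SD of the change score. The fMRI set may be smaller, because fMRI is not required for eligibility.

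**The case against.** The strongest reply is that the documents, taken whole, do plan a between-arm analysis. The path-analysis text models treatment against all secondary outcomes, and TMS and fMRI are secondary outcomes. A regression of a marker on treatment estimates an arm effect wherever it is printed. The comparison across conditions may also mean arms. The sentence in the Specific Aims names no paired test and no rule for claiming superiority, and could be read as saying when markers are measured. Finally, these outcomes are secondary and declared exploratory.

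Much of this stands. A reader might infer that the trial cannot test the Aim 2 hypothesis, or that it throws away the randomised comparison. The documents do not support either, because the planned regression is an arm-level analysis.

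The reply does not supply an Aim 2 test, however. The regression is introduced to complete a path analysis of pain, is not tied to Aim 2, and leaves open the marker's baseline and the three contrasts that the hypothesis needs. Exploratory status governs how strongly a result is claimed. It does not make a within-arm comparison answer a between-arm question.

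**Conclusion.** The point holds as a mismatch and an under-specification. The comparison worded for Aim 2 does not test its hypothesis, and the Aim 2 analysis text names no between-arm model or contrast to do so.

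Under the assumptions above, and if a significant result beside a non-significant one were read as a difference, a misleading contrast against one given comparator would arise in 16% to 25% of trials. A pattern that appears to confirm the whole hypothesis would arise in about 1% to 6%. The plan states no such decision rule, so these are illustrations of the risk and not predicted error rates.

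A reader might instead count trials in which the combined arm is significant and at least one comparator is not: p(1 − p³) = 44%, 47% and 39% at the three power values. The arithmetic is right, but the stated hypothesis requires superiority over all three comparators, so that figure is not the rate of false confirmation and should not be quoted as such.

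The logical point does not depend on the power values. The primary endpoint and sample size are not affected.

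**What to change.** Replace the before-after sentence in Aim 2, and add to the text for aim 2 a between-arm model for each key TMS and fMRI marker:

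- **Outcome:** the post-treatment value at a named visit. TMS is scheduled at more than one visit after treatment starts (Visits 13, 14 and 17), so the visit needs stating.
- **Terms:** arm, or tDCS, mirror therapy and their interaction.
- **Adjustment:** the baseline value of the marker and the randomisation strata, namely the baseline-pain stratum, and centre where applicable. The plan names a single imaging centre for fMRI.
- **Contrasts:** combined minus each of the other three arms, with confidence intervals. With 0/1 coding of the factors these are: mirror therapy + interaction (against tDCS alone); tDCS + interaction (against mirror therapy alone); and tDCS + mirror therapy + interaction (against double sham). The interaction coefficient alone is not the hypothesis.

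Keep within-arm changes as descriptive summaries and leave the analyses secondary and exploratory. State what is meant by conditions in the fMRI comparison, and whether the 7 to 8 subjects refer to a within-arm or a between-arm change.

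The cost is analysis wording, a little more analysis work, and the loss of within-arm p-values as evidence. The measurements needed are already in the visit schedule.

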#### IV. SUBJECT SELECTION

In this study, we will recruit 132 subjects with phantom limb pain (PLP) of traumatic etiology (congenital or diabetic amputees will be excluded since these patients may have a different neuroplastic profile). The subjects will be recruited by 2 main neurorehabilitation study centers, one at neuromodulation center - Spaulding rehabilitation Hospital and one at University of Sao

Paulo Brazil (IMREA). Subjects will need to meet all of the following inclusion criteria and none of the following exclusion criteria:

**Inclusion Criteria:**

1. Able to provide informed consent to participate in the study.
2. Subject is older than 18 years.
3. Unilateral lower limb amputation.
4. 3 months of phantom limb pain (experienced regularly for at least once a week) after the amputated limb has completely healed.\*
5. Average pain of at least 4 on a numeric rating scale in the previous week (NRS; ranging from 0 to 10).
6. If the subject is taking any medications, dosages must be stable for at least 2 weeks prior to the enrollment of the study.

[figure not shown]
\*The healing status of the limb will need to be confirmed by the subject's physician or by the physician of the protocol [name] (Co-Investigator).

[figure not shown]
**Exclusion Criteria:**

1. Pregnancy or trying to become pregnant in the next 2 months.
2. History of alcohol or drug abuse within the past 6 months as self-reported.
3. Presence of the following contraindication to transcranial direct current stimulation and transcranial magnetic stimulation
  - Ferromagnetic metal in the head (e.g., plates or pins, bullets, shrapnel)
  - Implanted neck or head electronic medical devices (e.g., cochlear implants, vagus nerve stimulator)
4. Head injury resulting in permanent neurological deficits, such as cognitive or motor deficits, as self-reported.\*
5. Unstable medical conditions (e.g. uncontrolled diabetes, uncompensated cardiac issues, heart failure or chronic obstructive pulmonary disease)
6. Uncontrolled epilepsy or prior seizures within the last 1 year
7. History of unexplained fainting spells or loss of consciousness as self-reported during the last 2 years.
8. History of neurosurgery, as self-reported.
9. Mirror Therapy within 3 months prior to enrollment

\* permanent neurological deficit that may interfere with the assessments.

The safety of tDCS in pregnant population (and children) has not been assessed and therefore pregnant women (and children) will be excluded. Women of child-bearing potential will be required to take a urine pregnancy test during the screening process.

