## **V. STUDY PROCEDURES**

We will recruit 132 participants with major lower unilateral limb amputation and phantom limb pain in the chronic phase.

The patients will be assigned to one of four groups: the first will receive active tDCS and active MT; the second will receive sham tDCS and active MT; the third will receive active tDCS and sham MT; and the fourth will receive both sham tDCS and sham MT. Subjects and outcome evaluators will be blinded to the intervention assigned. The study will be done for a total of 13 weeks. The study procedures will be done in the same way in both study centers. Data collection will be performed according to the IRB approved protocol by trained and capable research staff. The Neuromodulation Center (Spaulding Rehabilitation Hospital) will be responsible for providing training and responsible for monitoring of the study, including maintaining regular contact with the University of Sao Paulo site through telephone contact. This phone contact will be logged and stored at the Regulatory binder. The data will be collected by staff members (PI, co-investigators and study staff) familiar with the protocol and the tDCS and TMS technology. The care, safety, and comfort of the subjects will be under the supervision of a physician and therapist at each trial site. The local IRB at each respective institution will be responsible for overseeing the conduct of the study trial locally. Both IRB institutions approved the research protocol. Unidentifiable data from the local institution in Brazil will be shared with the main site (Boston) via IRB approved data base RedCap. There will be no sharing of PHI between the sites.

The subjects randomized to receive sham tDCS and/or sham MT will have the opportunity to enroll into an open label portion of the study at the conclusion of their participation in the randomized portion of the trial, including 10 sessions of tDCS combined with MT and additional questionnaire data.

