*Side Effects Questionnaire for tDCS:* At each stimulation session, subjects will complete a questionnaire to evaluate potential adverse effects of tDCS (tingling, burning sensation, headache, neck pain, mood alterations) and mirror therapy (anxiety, grief, dizziness) on a 4-point scale (None, mild, moderate and severe). The subjects will be asked whether they have experienced any side effects in an open-ended manner and they will then be specifically asked about headache, neck pain, scalp pain, scalp burns, tingling, skin redness, sleepiness, trouble concentrating, and acute mood change. If any side effects are reported, the degree of relatedness to the intervention will be assessed on a 5-point scale. This type of adverse events questionnaire has been used frequently in our previous tDCS studies [31], including in patients with phantom limb pain [48].

*Side Effects Questionnaire for TMS:* At each TMS assessment session, subjects will complete a questionnaire to evaluate potential adverse effects of rTMS (headache, neck pain, itching and redness at the site of stimulation) on a 5-point scale [49].

*tDCS blinding questionnaire:* after the stimulation session, subjects will complete a questionnaire to determine if our blinding methods were effective. We are using a 30s sham montage, just as we use in our other trials, keeping the device on the subject for the duration of the session [50].

*Patient's Global Impression of Change scale:* subjects will complete a questionnaire to assess their perception of change (if any) in the activity limitations, symptoms, emotions and overall quality of life after their participation in intervention's visits of the trial [51].

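### Entry criteria screen out recent mirror therapy but not recent tDCS, although both are randomized factors; prior tDCS is neither excluded nor listed for recording

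*Combined protocol and SAP*

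**What the plan says.** Under Exclusion Criteria, item 9 reads "Mirror Therapy within 3 months prior to enrollment". Elsewhere in that list, tDCS appears only as a safety matter. Item 3 concerns "Presence of the following contraindication to transcranial direct current stimulation and transcranial magnetic stimulation" (head metal, implanted devices), and the closing paragraph explains why pregnant women and children are excluded.

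Under Inclusion Criteria, the one rule on concurrent or previous treatment is "If the subject is taking any medications, dosages must be stable for at least 2 weeks prior to the enrollment of the study". Entry also requires "Average pain of at least 4 on a numeric rating scale in the previous week".

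The pre-screening and screening steps in Study Outline do not mention earlier tDCS. Randomization is stratified by baseline pain and centre. The covariates listed under Statistical Analysis, For aim 1, include centre, baseline pain, psychological and functional changes, and treatment.

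On durability, Specific Aims describes "a final 8-week follow-up period without any treatment to examine long-lasting effects of each therapy". On masking, Study Procedures says "Subjects and outcome evaluators will be blinded to the intervention assigned", and the entry for the tDCS blinding questionnaire says "We are using a 30s sham montage, just as we use in our other trials". The primary outcome is phantom limb pain rated by the subject on a VAS.

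**The concern.** By excluding recent MT, the plan accepts that recent exposure to a randomized therapy can be a reason to keep a subject out. It gives no reason for applying this to one factor only. As written, a person who finished a tDCS course last week is eligible.

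Two things are at stake, and they need not act in the same direction:

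- **Carry-over.** A subject who still benefits from earlier tDCS may improve less on active stimulation, or may hold a residual benefit while on sham. Either way the active-sham difference shrinks. That difference, with a visual therapy in both arms, is the one on which the sample size was built.
- **Recognition.** Active stimulation lasts 20 minutes and the sham is a 30-second montage. Someone who knows how real stimulation feels may be more likely to guess the assignment. On a self-rated outcome this could enlarge the apparent effect.

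**Working it through.** **Is the gap closed elsewhere?** Each place where prior tDCS could be handled was checked.

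| Place | Mirror therapy | tDCS |
|---|---|---|
| Exclusion Criteria | Item 9, 3 months | Safety contraindications and pregnancy rationale only |
| Inclusion Criteria | – | Medication stability only |
| Pre-screening and Screening Procedures | – | Not listed |
| Randomization strata | – | Baseline pain and centre only |
| Covariates, For aim 1 | – | No prior-exposure term |

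The content of the phone screening questionnaire is not shown, so it may ask about tDCS. Even so, no listed criterion would act on the answer.

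**The plan's own sample size.** Inputs from Sample size calculation: means 5.2 and 6.4, SDs 1.5 and 1.6, two-sided alpha 0.05, power 80%.

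- Difference: 6.4 − 5.2 = 1.2.
- Pooled SD: √[(1.5² + 1.6²)/2] = √2.405 = 1.551.
- Standardized difference: 1.2/1.551 = 0.774.
- Normal approximation: n per arm = 2 × [1.551 × (1.960 + 0.842)/1.2]² = 26.2, rounded up to 27; 4 × 27 = 108. This agrees with the plan.
- Attrition: 27 × 1.2 = 32.4, rounded up to 33; 4 × 33 = 132. This also agrees.
- Power at 27 per arm: 81.1% by the normal approximation, 79.7% by the two-sample t calculation. The t figure is used below.

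**Illustration of dilution.** Let f be the share of entrants with carry-over (the same in both arms, as randomization gives in expectation) and k the fraction of the tDCS effect that they can still show. With the SD unchanged, the expected difference is 1.2 × [1 − f(1 − k)]. The documents give neither f nor k, so both are assumed.

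| f | Subjects out of 132 | Difference, k = 0.5 | Power | Difference, k = 0 (worst case) | Power |
|---|---|---|---|---|---|
| 0 | 0 | 1.20 | 79.7% | 1.20 | 79.7% |
| 5% | about 7 | 1.17 | 77.7% | 1.14 | 75.5% |
| 10% | about 13 | 1.14 | 75.5% | 1.08 | 70.9% |
| 20% | about 26 | 1.08 | 70.9% | 0.96 | 60.7% |

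At f = 2% (about 3 subjects), the worst case is 78.1%.

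These figures are for a single 27 v 27 pair. If the tDCS factor were instead tested by pooling over MT (54 v 54, same assumed difference), worst-case power would be 96.6%, 94.8% and 89.0% at f = 5%, 10% and 20%. The plan specifies a four-level group term with post-hoc comparisons, so the pooled figures are only a comparison.

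The effect of recognition on the contrast cannot be computed from the documents.

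**The case against.** The strongest case on the other side is that the gap may have almost no effect in practice.

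- **Evidence of exposed candidates is thin.** The side-effects questionnaire is said to be one that "has been used frequently in our previous tDCS studies [31], including in patients with phantom limb pain [48". A reader might infer a pool of previously stimulated phantom-limb patients. The documents do not support that: the sentence is about where a questionnaire was used, the first reference is by its title a spinal cord injury study, and the second is by its title a trial in HTLV-1. The population, traumatic unilateral lower-limb amputees, is narrow. What stands is that one of the two sites is a neuromodulation centre that refers to its other tDCS trials, so exposure is possible but uncounted.
- **Lasting effects are a question in this plan.** A reader might infer that the plan expects tDCS benefit to persist, because Visit 17 falls about ten weeks after the last stimulation (two weeks of home MT plus eight). The stated purpose is to examine durability, and no carry-over duration is given. Still, a plan that leaves the question open has not shown that recent tDCS is harmless.
- **There are partial safeguards.** The pain floor of 4 limits entry of subjects with large residual benefit, though not those with partial benefit. Randomization balances prior exposure in expectation, so carry-over dilutes the contrast and does not bias it systematically. The blinding questionnaire at Visits 13 and 17 can detect unblinding but cannot prevent it.
- **Recognition is asserted.** The documents do not show that experienced subjects can identify this sham. Part of the intervention description is missing from the available text, so the sham cannot be fully judged. A washout would not erase the memory of stimulation in any case.

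These points limit the size of the concern. None of them explains why one randomized factor has an exposure rule and the other has none.

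**Conclusion.** The concern holds as a gap in eligibility and data collection. Recent tDCS is not excluded, and no listed step would identify the exposed subjects afterwards.

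Its size is unknown. The loss is about 2 to 9 percentage points of power in one pairwise contrast (79.7% to between 77.7% and 70.9%) if 5% to 20% are exposed and half the effect remains. It is about 4 to 19 points (to between 75.5% and 60.7%) if they show no further effect. These ranges rest on assumed shares and assumed residual effects, equal exposure across arms and an unchanged SD. With only a few exposed subjects the loss is small.

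Two stronger readings should be set aside. One is that the tDCS comparison is biased towards the null: carry-over dilutes it, but recognition of sham could push it the other way, so the net direction is undetermined. The other is that the MT interval of 3 months, or a ban on every form of non-invasive brain stimulation, is the evident correction. The documents give no basis for either.

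**What to change.** 1. Make item 9 cover both randomized therapies by adding recent tDCS. The investigators should set and justify the interval.
2. Record any earlier tDCS, with its date, at screening. This is the part that addresses recognition, since subjects treated before the exclusion interval would still enter.
3. Pre-specify a sensitivity analysis that repeats the tDCS contrast and the blinding-questionnaire summary in tDCS-naive subjects.

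The cost is a short addition to one criterion, one screening question and one extra analysis. A few candidates would be deferred or not enrolled. The planned 108 evaluable and 132 enrolled do not change. The screening question should be in place before enrollment, because exposure that is not recorded then may not be reliably recoverable later.
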